4. ENDPOINTS

4.1. Primary Endpoints

The primary endpoints are:

- 50% inhibitory dilution (ID_{50}) titers of vaccine-induced neutralizing antibodies to the SARS-CoV-2 S protein assessed 56 days after the first dose of Moderna mRNA-1273 vaccine in individuals who receive high-dose (1200 mg) REGN10933+REGN10987 compared to vaccine alone
- 50% inhibitory dilution (ID_{50}) titers of vaccine-induced neutralizing antibodies to the SARS-CoV-2 S protein assessed 56 days after the first dose of Moderna mRNA-1273 vaccine in individuals who receive submaximal dose levels of REGN10933+REGN10987 (less than 1200 mg) compared to vaccine alone

4.2. Secondary Endpoints

The secondary endpoints are:

- Absolute values, change from baseline, and percentage change from baseline in concentrations of vaccine-induced antibodies to the following SARS-CoV-2 antigens over time:
 - Anti-S protein
 - Anti-RBD
 - Other S protein subdomains (including S1, S2, and NTD)
- 50% inhibitory dilution (ID_{50}) titers of vaccine-induced neutralizing antibodies to SARS-CoV-2 S protein assessed over time after the first dose of Moderna mRNA-1273 vaccine

- Proportion of subjects with treatment-emergent adverse events (TEAEs) throughout the study
- Proportion of subjects with treatment-emergent serious adverse events (SAEs) throughout the study
- Proportion of subjects with infusion-related reactions (grade ≥ 2) to REGN10933+REGN10987 through day 4 post-infusion
- Proportion of subjects with injection site reactions (grade ≥ 3) to REGN10933+REGN10987 or each dose of Moderna mRNA-1273 vaccine through day 4 post-injection
- Proportion of subjects with hypersensitivity reactions (grade ≥ 2) to REGN10933+REGN10987 or each dose of Moderna mRNA-1273 vaccine through day 29 post-infusion or post-injection (as applicable)
- Concentrations of REGN10933 and REGN10987 in serum over time
- Immunogenicity, as measured by anti-drug antibodies (ADA) and neutralizing antibodies (NAb) to REGN10933 and REGN10987

4.3. Exploratory Endpoints

The exploratory endpoints are:

- Absolute percentages, change, and percentage change from baseline of blood-derived memory T cell responses specific to SARS-CoV-2 viral peptides over time
- Absolute percentages, change, and percentage change from baseline of blood-derived B cell responses specific to SARS-CoV-2 S protein, RBD, and other S protein subdomains over time
- Viral variant characteristics of SARS-CoV-2 in subjects who become infected post-baseline

5. STUDY VARIABLES

5.1. Demographic and Baseline Characteristics

Baseline characteristics will include standard demography (eg, age, race, weight, height, etc), medical history, and medication history for each subject.

5.2. Pharmacodynamic and Other Biomarker Variables

Primary, secondary, and exploratory endpoint variables may include, but are not limited to, the following: parameters reported in neutralization antibody titer assays to SARS-CoV-2 variants, binding antibody assays to SARS-CoV-2 antigens, virus-specific T cell and B cell assays, assays for detection of antibodies binding to RBD elicited post-vaccination that compete with REGN10933 and/or REGN10987, virology tests, and virus sequencing for variant determination.

5.3. Safety Variables

Safety variables include recording, measurements, or laboratory test results for individual subjects of the following: Adverse events (AEs), vital signs (including temperature, blood pressure, heart rate, and respiratory rate), targeted physical examination findings, and results of laboratory tests (including hematology, blood chemistry, urinalysis, and pregnancy test).

5.4. Pharmacokinetic Variables

The variables are the concentration of REGN10933 and REGN10987 in serum, and time. Samples will be collected at the visits specified in the Schedules of Events (Section 9.1).

5.5. Immunogenicity Variables

The study drug immunogenicity variables are ADA status, titer, NAb status, and time point/visit. Samples will be collected at the visits specified in the Schedules of Events (Section 9.1).

6. STUDY DESIGN

This study is a phase 2, randomized, open-label, parallel group study in healthy adult volunteers to assess the immunogenicity, safety, and tolerability of Moderna mRNA-1273 vaccine when administered with REGN10933+REGN10987.

6.1. Study Description and Duration

The study consists of 3 periods: a screening/baseline period, a vaccine response assessment period, and a follow-up period. The study design is depicted in [Figure 2](#) and [Figure 3](#); study treatment assignment is depicted in [Figure 1](#). The Schedules of Events can be found in [Table 3](#) (enrollment wave 1 [study arms 1, 2, 3, and 6a] and enrollment wave 3 [arms 7, 8, and 6c]), [Table 4](#) (enrollment wave 2 [study arms 4, 5, and 6b]), and [Figure 3](#) (enrollment wave 4 [arms 9 and 6d]).

Subjects will be assessed for eligibility during the **screening/baseline period**, which may occur up to 21 days prior to day 1. To be eligible for the study, subjects must be confirmed negative for current or past SARS-CoV-2 infection by both RT-PCR and serology tests (refer Section [7.2.2](#) for exclusion criteria).

During this period, subjects will also be assigned to an enrollment wave, as described in Section [8.5](#).

On day 1, eligible subjects will be randomized to a study arm (1 of 12) within their assigned enrollment wave. Subjects randomized to study arms 1 through 5 or 7 through 9 will receive an IV infusion or SC injection of the study drug (REGN10933+REGN10987) on day 1 or day 7. Subjects in arms 6a to 6d (the control arms) will not receive any study drug. The first dose of the vaccine will be administered on day 1 or day 15, based on study arm assignment at randomization ([Figure 1](#)).

All subjects will receive the second dose of the vaccine 28 days after their first dose of the vaccine in accordance with the EUA Fact Sheet ([Moderna COVID-19 Vaccine \[HCP Fact Sheet\], 2022](#)) (refer to Section [3.2.1](#) for rationale). Refer to Section [8.5](#) for more information on dose levels and timing of administration.

The **vaccine response assessment period** represents the time period of the primary analysis (Section [4.1](#)). For study arms 1, 2, 3, 7, 8, 6a, and 6c, this period includes up to study day 71; for study arms 4, 5, 9, 6b, and 6d, the period includes up to day 57. Following this assessment period, subjects will enter a **follow-up period** lasting up to 10 months.

Throughout the study, blood samples will be collected to assess whether the study drug impacts the ability of the vaccine to elicit neutralizing antibody titers against the SARS-CoV-2 S protein, and to understand any impact on vaccine-induced humoral and cellular immune responses to various S protein epitopes. Additional details are provided in Section [9.2.3](#).

Subjects will also have blood samples taken at select visits for drug concentration, immunogenicity, and exploratory analyses, and will be monitored for AEs (including AESIs) during in-person visits (refer to Section [10.1](#) for recording and reporting requirements). For subjects in study arms 4 and 5 (receiving the study drug and vaccine on the same day), a phone call will be made within 24 hours following study drug and vaccine administration on day 1 for AE collection.

The last study visit will take place approximately 1 year after the first dose of the vaccine.

Vaccine booster sub-study. All subjects who have not already received the COVID-19 vaccine booster will be offered an optional booster vaccination dose ≥ 5 months after completing the primary COVID-19 vaccination series and >35 days (ie, until study day 345 for subjects in arms 1, 2, 3, 6a, 6c, 7 and 8 and until study day 331 for subjects in arms 4, 5, 6b, 6d and 9) before the end of the main study. Blood samples for possible analysis will be collected pre- and post-booster administration.

Figure 2: Study Flow Diagram (Enrollment Waves 1 and 2)

[figure not shown]
[figure not shown]

Figure 3: Study Flow Diagram (Enrollment Waves 3 and 4)

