3.2.1.8. Safety and Tolerability

REGN10933+REGN10987, when given concomitantly or in temporal proximity to Moderna mRNA-1273, is reasonably expected to be well-tolerated in healthy volunteers (see Section 3.1). Nevertheless, this study will evaluate safety and tolerability of REGN10933+REGN10987 and Moderna mRNA-1273, including assessment of IRR (REGN10933+REGN10987) as well as ISR and hypersensitivity reactions (REGN10933+REGN10987 and Moderna mRNA-1273; see Section 4).

As a precautionary safety measure, a follow-up phone call will be made within 24 hours after study drug and vaccine administration, for subjects receiving these concomitantly (see Section 9.2.2).

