7. Note that not all subjects will receive study drug at randomization. Refer to Section 8.5 and Figure 1 for more information.

Study arms 4 and 5: Subjects assigned to study arms 4 and 5 will receive both the study drug and vaccine on day 1. The study drug will be administered first, followed by the vaccine. There must be a minimum of 2 hours waiting period between administration of the study drug and subsequent vaccine administration. Approximately 24 hours after completion of the study drug and vaccine administration on day 1, subjects will be followed up by telephone for safety. Subjects should be monitored for at least 1 hour after study drug or vaccine administration.

Study arms 6a, 6b, 6c, and 6d only: Subjects assigned to one of these study arms will not receive study drug. These subjects will receive the vaccine only. These subjects should be monitored for at least 30 minutes after vaccine administration.

Refer to Section 9.2.2 for additional information concerning administration and monitoring requirements following study drug and/or vaccine administration.

8. Serology characterization assays will be used to assess antibodies against various SARS-CoV-2 antigens including: S protein, RBD, S1, and N protein. Refer to Section 9.2.3.1, Section 9.2.3.2, and Section 9.2.3.3 for more information on procedures and assays related to vaccine response assessment.
9. Vital signs, including temperature, blood pressure, heart rate, and respiratory rate will be collected prior to and 30 minutes following each administration of the study drug or vaccine primary series (first and second dose) as described in Section 9.2.4.1.
10. Actual dosing time and drug concentration sample collection times will be recorded.

Study arms 1, 2, 3, 7, 8, and 9 (receiving IV infusion of study drug): At the indicated visit, blood for assessment of drug concentration in serum will be taken prior to dosing and within 60 minutes after the end of infusion (EOI). The EOI sample should be collected from the arm contralateral to that used for IV infusion. If not medically feasible, the EOI sample can be drawn from the same arm, but not from the infusion catheter.

Study arms 4 and 5 (receiving SC injection of study drug): At the screening/baseline visit, blood for assessment of drug concentration in serum will be taken prior to dosing. The post-dose blood collection should occur at least 1 hour after study drug administration.

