9.2.2. Study Drug and Vaccine Administration and Post-Administration Monitoring

Refer to Section 8.5 for treatment assignments.

SC and IM Injection Administration

All subjects allocated to a SC regimen will receive either 4 (study arm 4) or 2 (study arm 5) injections of study drug on the day of administration. It is recommended that SC injection sites should be chosen among the different quadrants of the abdomen (avoiding navel and waist areas) and upper thighs. During study drug administration, each injection must be given in a different anatomical location (1 injection administered in the right lower quadrant of the abdomen, another in the left lower quadrant of the abdomen, etc).

All subjects will receive each Moderna mRNA-1273 vaccination dose through a single IM injection in the deltoid muscle ([CDC, 2021](#)).

Subjects should receive all doses of Moderna mRNA-1273 vaccine as assigned and as described in the EUA Fact Sheet ([Moderna COVID-19 Vaccine \[HCP Fact Sheet\], 2022](#)).

Study arms 4 and 5 only: Subjects will receive both study drug and vaccine on day 1. The study drug will be administered first, followed by the vaccine. There must be a minimum of 2 hours waiting period between administration of the study drug and subsequent vaccine. Administration of the individual regimens should be performed as described above.

Post-administration monitoring of study drug and vaccine

Study arms 1 through 5 and 7 through 9: Subjects should be monitored for at least 1 hour after study drug or vaccine administration. Vaccine recipients should be monitored for the occurrence of acute reactions according to the latest CDC guidelines ([CDC, 2021](#)). For study arms 4 and 5 (receiving study drug and vaccine on the same day), approximately 24 hours after completion of the study drug and vaccine administration on day 1, subjects will be followed up by telephone for safety.

Study arms 6a, 6b, 6c and 6d: Subjects assigned to each of these study arms will not receive study drug during this study. These subjects should be monitored for at least 30 minutes after vaccine administration.

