10. SAFETY EVALUATION AND REPORTING

10.1. Recording and Reporting Adverse Events

10.1.1. General Guidelines

In this study, the following TEAEs will be recorded:

- Treatment-emergent AEs throughout the study
- Treatment-emergent SAEs throughout the study
- Treatment-emergent AESIs (defined in Section 10.1.3)

The investigator must promptly record all clinical events occurring during the study data collection, from the time of signing the ICF to the end of the post-vaccination observation period (see Section 11.4.6.1). Medical conditions that existed or were diagnosed prior to the signing of the Informed Consent will be recorded as part of medical history. Abnormal laboratory values and vital signs observed at the time of Informed Consent should also be recorded as medical history. Any subsequent worsening (ie, any clinically significant change in frequency and/or intensity) of a pre-existing condition that is temporally associated with the use of the study drug should also be recorded as an AE.

At each visit, the investigator will determine whether any AEs have occurred by evaluating the subject. Adverse events may be directly observed, reported spontaneously by the subject, or by questioning the subject at each study visit. Subjects should be questioned in a general way, without asking about the occurrence of any specific symptoms. The investigator must assess all AEs to determine seriousness, severity, and causality, in accordance with the definitions in Section 10.1.4. The investigator's assessment must be clearly documented in the site's source documentation with the investigator's signature. The investigator should follow up on SAEs (and AESIs) until they have resolved or are considered clinically stable; AEs should be followed until they are resolved or last study visit, whichever comes first.

Always report the diagnosis as the AE or SAE term. When a diagnosis is unavailable, report the primary sign or symptom as the AE or SAE term with additional details included in the narrative until the diagnosis becomes available. If the signs and symptoms are distinct and do not suggest a common diagnosis, report them as individual entries of AE or SAE.

Laboratory results, vital signs, and other diagnostic results or findings should be appraised by the investigator to determine their clinical significance. Isolated abnormal laboratory results, vital sign findings, or other diagnostic findings (ie, not part of a reported diagnosis) should be reported as

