5.8.1. Adverse Events

All AEs reported in this study will be coded using the currently available version of MedDRA®. Coding will be to lowest level terms. The PT and the primary SOC will be listed.

All adverse events will be provided in a listing. Listing of deaths and other SAEs will also be provided.

Tabulations by treatment group will include the following:

All periods combined

- Overview of TEAEs
- TEAEs by SOC and PT
- TEAEs by SOC and PT and Severity
- Serious TEAEs by SOC and PT
- Study Drug Related TEAEs by SOC and PT
- Vaccine Related TEAEs by SOC and PT
- Study Drug Related Infusion Related Reaction TEAEs by SOC and PT

- Study Drug Related Injection Site Reaction TEAEs by SOC and PT
- Vaccine Related Injection Site Reaction TEAEs by SOC and PT
- Study Drug Related Hypersensitivity Reaction TEAEs by SOC and PT
- Vaccine Related Hypersensitivity Reaction TEAEs by SOC and PT
- Treatment-Emergent AESIs by SOC and PT
- TEAEs leading to permanent discontinuation of vaccine by SOC and PT
- TEAEs leading to permanent discontinuation of study drug by SOC and PT
- TEAEs leading to death by SOC and PT

Pre-vaccination period

- Overview of TEAEs
- TEAEs by SOC and PT
- TEAEs by SOC and PT and Severity
- Serious TEAEs by SOC and PT
- Study Drug Related TEAEs by SOC and PT
- Study Drug Related Infusion Related Reaction TEAEs by SOC and PT
- Study Drug Related Injection Site Reaction TEAEs by SOC and PT
- Study Drug Related Hypersensitivity Reaction TEAEs by SOC and PT
- TEAEs leading to permanent discontinuation of study drug by SOC and PT
- TEAEs leading to death by SOC and PT

Primary series vaccination period and Post-booster vaccination period

- Overview of TEAEs
- TEAEs by SOC and PT
- TEAEs by SOC and PT and Severity
- Serious TEAEs by SOC and PT
- Study Drug Related TEAEs by SOC and PT
- Vaccine Related TEAEs by SOC and PT
- Study Drug Related Infusion Related Reaction TEAEs by SOC and PT
- Study Drug Related Injection Site Reaction TEAEs by SOC and PT
- Vaccine Related Injection Site Reaction TEAEs by SOC and PT
- Study Drug Related Hypersensitivity Reaction TEAEs by SOC and PT
- Vaccine Related Hypersensitivity Reaction TEAEs by SOC and PT

- TEAEs leading to permanent discontinuation of vaccine by SOC and PT
- TEAEs leading to permanent discontinuation of study drug by SOC and PT
- TEAEs leading to death by SOC and PT

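### Arms 4 and 5 get a 24-hour adverse-event call that control arm 6b does not, so mild first-dose events are ascertained more actively in the drug arms

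*Protocol*

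**What the plan says.** **The call.** Protocol 6.1 limits it by arm: "For subjects in study arms 4 and 5 (receiving the study drug and vaccine on the same day), a phone call will be made". The same sentence sets its timing and purpose: "a phone call will be made within 24 hours following study drug and vaccine administration on day 1 for AE collection". Section 3.2.1.8 gives the reason as a safety precaution: "a follow-up phone call will be made within 24 hours after study drug and vaccine administration, for subjects receiving these concomitantly". Footnote 7 in Section 9.1.1 says of arms 4 and 5 that "subjects will be followed up by telephone for safety". The paragraph on arms 6a to 6d in the same footnote has no such contact.

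**Observation on site.** Section 9.2.2 says of the drug arms: "Subjects should be monitored for at least 1 hour after study drug or vaccine administration". Of the control arms it says: "These subjects should be monitored for at least 30 minutes after vaccine administration".

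**Visits and questioning.** Arms 4, 5 and 6b share one schedule (Protocol Table 4), and the first visit after day 1 is day 15 ±2. Section 10.1.1 sets the style of enquiry for everyone: "Subjects should be questioned in a general way, without asking about the occurrence of any specific symptoms". Neither document describes a diary or a solicited-reaction form. Section 6.1.1 instructs all subjects to telephone the site if their health changes.

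**Analysis.** The proportion of subjects with TEAEs is a secondary endpoint (Protocol 4.2). SAP 5.8.1 tabulates TEAEs by treatment group for all periods combined and for the primary series vaccination period. The tables include vaccine-related TEAEs and "Vaccine Related Injection Site Reaction TEAEs by SOC and PT". Nothing in SAP 5.8.1 mentions the unequal contact.

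**The concern.** Safety and tolerability of drug and vaccine given in close succession is a secondary objective, and arms 4 and 5 are the only arms dosed with both on the same day. The natural comparator is 6b, which is randomised concurrently and gets the same vaccine on the same day. If one group is asked about AEs about a day after dosing and the other about two weeks after, the first will tend to report more mild, transient events even when the true rates are equal. The difference would show in the by-group tables and could be mistaken for an effect of adding the drug. Pooling 6a to 6d as one vaccine-alone group does not remove it, because none of them is called. The longer minimum observation in the drug arms adds a smaller difference in the same direction.

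**Working it through.** The plan gives no figure to reproduce on this point. The check has two parts.

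**1. Contact after the day 1 doses in wave 2**

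| | Arms 4 and 5 (30 + 30) | Arm 6b (15) |
|---|---|---|
| Day 1 products | SC drug, then vaccine at least 2 hours later | Vaccine |
| Minimum observation | 1 hour | 30 minutes |
| AE call at about 24 hours | Yes | No |
| Told to phone the site if health changes | Yes | Yes |
| Next scheduled AE enquiry | Day 15 ±2 | Day 15 ±2 |
| Call after second vaccine dose (day 29) | No | No |

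The asymmetry is therefore confined to the first dose.

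**2. Illustrative size**

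The documents give neither a reaction rate nor a recall rate, so every input here is an assumption.

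- *p* = true risk of a mild early event after a dose, equal in all arms: 0.40 to 0.80.
- *L* = share of such events lost when there is no call: 0.10 to 0.30. Nothing is lost with the call.
- The second dose has the same *p*, and loss *L* in every arm, because nobody is called. Events after the two doses are independent.

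For the first dose alone, the spurious excess is *p* × *L*. It runs from 0.40 × 0.10 = 4 points to 0.80 × 0.30 = 24 points.

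SAP 5.8.1 has no first-dose table. The primary series period runs to 28 days after the second dose (SAP 4.6.1), and a subject counts once. Write *q* = *p*(1 − *L*) for the chance that an event is recorded without a call.

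- Called arms: P(at least one recorded) = 1 − (1 − *p*)(1 − *q*)
- Uncalled arm: P(at least one recorded) = 1 − (1 − *q*)²
- Difference = (1 − *q*)(*p* − *q*) = *p* × *L* × [1 − *p*(1 − *L*)]

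| *p* | *L* = 0.10 | *L* = 0.30 |
|---|---|---|
| 0.40 | 0.04 × 0.64 = 2.6 points | 0.12 × 0.72 = 8.6 points |
| 0.60 | 0.06 × 0.46 = 2.8 points | 0.18 × 0.58 = 10.4 points |
| 0.80 | 0.08 × 0.28 = 2.2 points | 0.24 × 0.44 = 10.6 points |

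The range is about 2 to 11 points. Positive correlation between a subject's two doses would reduce it further.

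For scale, take *p* = 0.60 and *L* = 0.30. The recorded proportions are 1 − 0.40 × 0.58 = 0.768 in the called arms and 1 − 0.58² = 0.664 in 6b. The 95% half-width for 60 v 15 is 1.96 × √(0.768 × 0.232/60 + 0.664 × 0.336/15) = 0.26. The artefact is smaller than the sampling error, but under these assumptions it always points the same way.

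With the same call in 6b, both arms record the first dose with the same probability, and the spurious difference is zero for any *p*.

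**The case against.** **The call has a sound safety purpose.** It does, and it should stay. That does not make the resulting counts comparable with an arm that was not called.

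**Other routes catch events in 6b.** Subjects are told to phone the site, AEs are monitored continuously (footnote 12), and everyone is asked at day 15. This stands in part: capture in 6b is lower, not absent. Serious events, grade 3 or higher injection-site reactions and grade 2 or higher hypersensitivity reactions are unlikely to be lost.

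**The comparison is descriptive and the bias cannot hide harm.** No hypothesis test is planned, the primary titre endpoint is untouched, and over-counting mild events in the drug arms is conservative for safety. This stands and limits the severity. By-group percentages will still be read side by side.

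**Arms 4 and 5 v 6b is not a clean contrast in any case.** A reader might infer that both groups start the TEAE clock with the same injection. They do not. Arms 4 and 5 receive SC drug first, so their clock starts with the drug, while that of 6b starts with the vaccine. There is no placebo injection and the study is open-label. Equal calls would remove one difference, not all of them.

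**Vaccine reactions may last long enough to be recalled.** A reader might apply the statement in Protocol 3.3.1 that most injection-site reactions arose within a day and resolved within two. It concerns the SC antibody in another trial, and the documents give no durations for the vaccine's listed side effects. Brevity of vaccine reactions is therefore an assumption here.

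**It is too late to call 6b, and dropping call-recorded events over-corrects.** Both points have force. The Amendment 5 rationale reports an interim analysis that already included wave 2. On the assumed recall loss, 70% to 90% of the dropped events would have been reported at day 15 anyway. The restricted table is therefore a bound, not a corrected estimate.

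**Conclusion.** The asymmetry is explicit in the protocol and its direction is clear: mild, short-lived, non-serious first-dose events are ascertained more actively in arms 4 and 5 than in 6b or any other control arm, and SAP 5.8.1 makes no allowance for it. The size cannot be derived from the documents. On the assumptions listed, it is about 2 to 11 percentage points in a two-dose table. The 4 to 24 points for the first dose alone correspond to no table that the SAP plans.

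A reader might go further and infer that the whole tolerability comparison is unsound, or that an excess seen only with call-recorded events is not a drug-vaccine effect. The documents support neither. The second dose, serious events and higher-grade reactions are essentially unaffected, and acute reactions to same-day dosing are exactly what the call is meant to detect. This is a worthwhile, inexpensive improvement to a secondary descriptive comparison.

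**What to change.** **If any 6b subject is still to be dosed on day 1:** add 6b to the 24-hour AE call in Protocol 6.1, Section 9.2.2 and footnote 7, and carry the change into the synopsis, Section 3.2.1.8, SAP 2.3 and SAP Appendix 11.1. The timing wording should be reconciled at the same time: Section 6.1 puts the call within 24 hours, while Section 9.2.2 and footnote 7 put it at approximately 24 hours. Cost: at most 15 short calls.

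**For subjects already past day 1:** amend SAP 5.8.1 as follows.

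- Flag each AE first recorded at the call.
- Show the TEAE and injection-site-reaction tables for arms 4 and 5 v vaccine alone twice: in full, and without the non-serious flagged events. Label the second as over-correcting, so that the pair brackets the ascertainment artefact.
- State beside the tables that only arms 4 and 5 were called and that minimum on-site observation differed between drug and control arms.
- Set no rule that discounts an excess seen only with call-recorded events.

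Cost: one extra version of two safety tables and a footnote. It requires that call-recorded events can be identified in the data; if they cannot, the disclosure should stand alone.
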